To assess their eligibility to enter the study, potential subjects will be screened within 28 days (Days -29 to -2) and be admitted to the Clinical Research Unit (CRU) on Day -1 (Check-in). Replacement subjects may be enrolled only if deemed necessary by the Sponsor.

Subjects will be confined at the CRU from the time of Check-in (Day -1) until End of Treatment (EOT) on Day 30 upon completion of all PK and safety assessments or Early Termination (ET) if the subject discontinues. A follow-up phone call will occur for all subjects who received at least 1 dose of study drug (including subjects who are terminated early) 7 days (\pm 2 days) after EOT or ET.

The start of the study is defined as the date the first subject who is enrolled in the study signs an Informed Consent Form (ICF). Note that enrolled subjects are defined as those subjects who are assigned a dose of study drug; this definition excludes screen failure subjects.

In this study, PEs, 12-lead ECGs, vital signs, How Do You Feel? (HDYF?) inquiries, clinical chemistry panel, coagulation parameters, complete blood count (CBC), and urinalysis (UA; [Appendix 2](#)) and recording of concomitant medications will be performed at specified times during the study (for specific timepoints and details on each study variable, refer to [Appendix 4](#)). AEs and SAEs will be collected beginning at informed consent. AEs will be reported throughout the study (ie, from signing of the ICF until End of Study [EOS], or until ET if the subject discontinues from the study and does not complete a follow-up phone call), either as subject medical history (if the event is reported as beginning prior to signing of the ICF or if the event occurs prior to study drug administration on Day 1 and is assessed as not related to study procedures by the Investigator [or designee]) or as AEs (if the event occurs after signing of the ICF but prior to study drug administration on Day 1 and is assessed as related to study procedures by the Investigator [or designee], or if the event occurs after study drug administration on Day 1 through EOT or ET regardless of relationship to study drug). From EOT or ET through EOS, only AEs assessed as related to study drug by the Investigator (or designee) are to be reported. All SAEs that develop from the time of ICF signing until EOS (or ET, if the subject discontinues from the study and does not complete a follow-up phone call) are to be reported.

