7.2.1. Adverse Events

Adverse event definitions; assignment of severity, causality, action taken, and outcome; and procedures for reporting SAEs are detailed in [Appendix 1](#).

Subjects will be asked a nonleading HDYF? question such as “Have there been any changes in your health status since Screening/since you were last asked?” at the timepoints specified in [Appendix 4](#) (ie, at Screening [after the ICF is signed], at Check-in (Day -1), at each postdose vital signs assessment, and at an appropriate time for all other days). Subjects will also be encouraged to voluntarily report AEs occurring at any other time through the EOS.

AEs, whether volunteered, identified by the subject’s responses to HDYF? inquiries, or noted on PE, ECG, vital signs assessments, or laboratory tests, will be recorded throughout the study (ie, from signing of the ICF until EOS [or ET if the subject discontinues from the study and does not complete a follow-up phone call]), either as subject medical history (if the event is reported as beginning prior to signing of the ICF or if the event occurs prior to study drug administration on Day 1 and is assessed as not related to study procedures by the Investigator [or designee]) or as AEs (if the event occurs after signing of the ICF but prior to study drug administration on Day 1 and is assessed as related to study procedures by the Investigator [or designee], or if the event occurs after study drug administration on Day 1 through EOT or ET regardless of relationship to study drug). From EOT or ET through EOS, only AEs assessed as related to study drug by the Investigator (or designee) are to be reported. All SAEs that develop from the time of ICF signing until EOS (or ET, if the subject discontinues from the study and does not complete a follow-up phone call) are to be reported.

Unless a subject withdraws consent or is withdrawn from the study and does not complete the follow-up phone call, all subjects must be followed until EOS. Subjects with AEs that are assessed as related to study drug by the Investigator (or designee) which are ongoing at EOS may continue to be followed until the symptoms or value(s) return to normal, or acceptable levels, as

judged by the Investigator or designee and confirmed by the Sponsor. The Investigator (or designee) should use appropriate judgment in ordering additional tests as necessary to monitor the resolution of events. The Sponsor may request that additional safety tests be performed.

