^p Prior and concomitant medication administration will be recorded beginning at informed consent. In addition, all Investigator-approved medications taken by a subject within 30 days prior to study drug administration for prescription medications, and 14 days prior to study drug administration for nonprescription medications, will be recorded on the subject's electronic Case Report Form.

^q Female subjects only.

^r Postmenopausal female subjects only.

^s EOT is defined as when the subject is released from the CRU following completion of all assessments through Day 30. ET is defined as when the subject is released from the CRU if the subject terminates the study early. Vital sign, ECG, and safety laboratory results for serum chemistry, hematology, coagulation, and urinalysis are to be available for review by the Investigator or designee prior to subject release from the CRU at the EOT or ET visit.

^t To be performed 7 days (\pm 2 days) following EOT or ET. EOS is defined as when the CRU contacts the subject by a follow-up phone call 7 days (\pm 2 days) after the EOT visit or ET visit to determine if any SAE or study drug-related AE has occurred since the EOT or ET visit. All subjects who received LOXO-292 (including subjects who are terminated early) will be contacted.

Letter of Administrative Change (LOAC) No. 2
An Open-Label, 3-Period, Fixed Sequence Study to Evaluate the Effect of an
H2 Antagonist and a Proton Pump Inhibitor on the Single Dose
Pharmacokinetics of LOXO-292 in Healthy Adult Subjects

Protocol Date: 20 June 2019
Letter of Administrative Change (LOAC) Effective Date: 10 July 2019

Sponsor Reference Number: LOXO-RET-19075
Covance Study Number: 8412-056
IND Number: 133193

PPD

Description of Changes:

The purpose of this LOAC is to amend the text in Section 12.1, *Inclusion Criteria*, Sub-Section 12.1.1, *All Subjects* of the Protocol (dated 20 Jun 2019) to include bilateral tubal ligation as an acceptable form of sterilization for female study participants.

Section 12.1, *Inclusion Criteria*, Sub-Section, 12.1.1 *All Subjects* of the Protocol will be revised as follows:

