10.4 Safety and Tolerability Assessments

10.4.1 Adverse Events

An event is defined as an AE if the event occurs after signing of the ICF but prior to study drug administration on Day 1 and is assessed as related to study procedures by the Investigator [or designee]. A treatment-emergent AE (TEAE) is defined as an AE that occurs postdose or that is present predose and becomes more severe postdose. The AE severity and relationship are determined by the investigator at the site. The severity grade of each AE will be based on the National Cancer Institute's Common Terminology Criteria for Adverse Events (CTCAE, Version 5.0) 5-point severity scale (Grade 1, 2, 3, 4 and 5). Not all grades are appropriate for all AEs. Therefore, some AEs are listed within the CTCAE with fewer than 5 options for grade selection.

A TEAE occurring during or after Day 1 dosing and up to predose Day 8 will be assigned to treatment 160 mg LOXO-292. A TEAE occurring after Day 8 dosing and up to Day 11 will be assigned to 150 mg ranitidine. A TEAE occurring after Day 12 dosing and up to Day 19 predose will be assigned to 160 mg LOXO-292 + 150 mg ranitidine. A TEAE occurring after Day 19 dosing and predose Day 22 will be assigned to 40 mg omeprazole QD. A TEAE occurring after Day 23 dosing until Follow-up will be assigned to 160 mg LOXO-292 + 40 mg omeprazole QD.

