All AEs will be listed. The TEAEs will be summarized by treatment, severity, and relationship to the study drug. The frequency (the number of TEAEs, the number of subjects experiencing a TEAE, and the percentage of subjects experiencing a TEAE) of TEAEs will be summarized by treatment, and by Medical Dictionary for Regulatory Activities system organ class and preferred term. A frequency summary will be presented by day of onset across the multiple-dosing period. The summary and frequency TEAE tables will be presented for all causalities and for those TEAEs considered related to the study drug (those that have a relationship of "Related"). Any severe or serious AEs will be tabulated. For any AEs that change severity ratings for a given treatment, the AE will be included only once under the maximum severity rating in the summaries. If a TEAE decreases in severity grade, the new TEAE record with lesser severity will be counted as the same TEAE event of the previous record with worse severity under the same treatment group. Onset times postdose are calculated from the last dose administered. Discontinuations due to AEs will be listed.

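### SAP 10.4.1 counts TEAEs for LOXO-292 + omeprazole until Follow-up, but over 7 days for the other two LOXO-292 treatments, so one column has a longer window and two collection rules (minor)

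*SAP*

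**What the plan says.** SAP 10.4.1 assigns each TEAE to a treatment by its time of onset. The three rules for the LOXO-292 treatments are:

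- LOXO-292 alone: "A TEAE occurring during or after Day 1 dosing and up to predose Day 8 will be assigned to treatment 160 mg LOXO-292".
- LOXO-292 + ranitidine: "A TEAE occurring after Day 12 dosing and up to Day 19 predose will be assigned to 160 mg LOXO-292 + 150 mg ranitidine".
- LOXO-292 + omeprazole: "A TEAE occurring after Day 23 dosing until Follow-up will be assigned to 160 mg LOXO-292 + 40 mg omeprazole QD".

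Protocol 3.1 keeps subjects in the unit "until End of Treatment (EOT) on Day 30 upon completion of all PK and safety assessments". Protocol Appendix 4 places the end of study (EOS) at the call: "EOS is defined as when the CRU contacts the subject by a follow-up phone call 7 days", with a margin of 2 days either way, after EOT or early termination (ET).

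The collection rule changes at EOT. Under Protocol 7.2.1 an event counts as an AE "if the event occurs after study drug administration on Day 1 through EOT or ET regardless of relationship to study drug". After that, "From EOT or ET through EOS, only AEs assessed as related to study drug by the Investigator (or designee) are to be reported". SAEs of any causality are collected to EOS.

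SAP 10.4.1 then tabulates events, subjects and percentages of subjects by treatment: "The summary and frequency TEAE tables will be presented for all causalities and for those TEAEs considered related to the study drug". It states no common cut-off, no adjustment for time at risk and no separate follow-up category.

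**The concern.** The by-treatment TEAE tables are the planned display for the secondary objective, which covers LOXO-292 alone, with ranitidine and with omeprazole. A reader will look across the columns. One of them runs for about twice as long as the other two, and in the added part non-serious events enter only if judged related.

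The effect has a direction. Every non-serious event added after EOT is by rule a related one, and it can enter the omeprazole-combination column only. It adds to that column's related-TEAE count. It also raises the related share of all the column's TEAEs, because unrelated non-serious events from the same days are not reported. With 20 subjects, one extra subject moves a column by 5 percentage points (1/20).

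**Working it through.** The documents state no window length, so there is no planned figure to reproduce. I take Follow-up in the SAP to mean the protocol's follow-up call.

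**Inputs.** Window rules: SAP 10.4.1. EOT on Day 30: Protocol 3.1. Call 7 ± 2 days after EOT: Protocol 7.2.1 and Appendix 4. LOXO-292 half-life of about 24 hours: Protocol 1.3. Twenty subjects: Protocol synopsis. The 7-day related risk is not in the documents and is assumed.

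**Window lengths for completers**

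- LOXO-292 alone: 8 − 1 = 7 days.
- LOXO-292 + ranitidine: 19 − 12 = 7 days.
- Call: Day 30 + 7 ± 2 = Day 35 to 39.
- LOXO-292 + omeprazole: 35 − 23 = 12 days to 39 − 23 = 16 days (nominal 37 − 23 = 14).
- Ratio to 7 days: 12/7 = 1.7 to 16/7 = 2.3.

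**Split of the third window**

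- Day 23 to EOT: 30 − 23 = 7 days, all causalities. This matches the other two windows in length and rule.
- EOT to call: 35 − 30 = 5 days to 39 − 30 = 9 days, related events plus all SAEs.

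The whole imbalance therefore comes from the 5 to 9 days after EOT. After ET in Period 3 the call is timed from ET, so the window can be shorter than 12 days.

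**Possible size in the related-TEAE table.** Let p be the assumed related risk over 7 days, the same in every period.

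*Constant hazard:* risk over d days = 1 − (1 − p)^(d/7). At p = 10%: 1 − 0.9^(12/7) = 16.5%, and 1 − 0.9^(16/7) = 21.4%.

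*Hazard proportional to LOXO-292 exposure* (mono-exponential decline, half-life 1 day, absorption phase ignored): the cumulative hazard to day 16 relative to day 7 is (1 − 2^−16)/(1 − 2^−7) = 1.008. At p = 10%: 1 − 0.9^1.008 = 10.1%. The share of drug left at 168 hours is 2^−7 = 0.8%.

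| Assumed 7-day risk | Exposure-tracking hazard | Constant hazard, 12 to 16 days |
|---|---|---|
| 5% | 5.0% | 8.4% to 11.1% |
| 10% | 10.1% | 16.5% to 21.4% |
| 20% | 20.1% | 31.8% to 40.0% |
| 30% | 30.2% | 45.7% to 55.7% |

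In 20 subjects at p = 10%, 2.0 are expected in a 7-day column. The longer column would show 2.0 if the hazard follows exposure and 3.3 to 4.3 if it is constant.

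**The case against.** A reader might infer that the plan sets out to compare tolerability and that the longer window makes the comparison invalid. The documents do not support that. The secondary objective is to determine safety and tolerability under each condition. Protocol 8.4 plans no formal analysis of safety data and SAP 10.4.7 plans no inference. The comparisons named in SAP 10.3.3 are pharmacokinetic. No decision rests on these percentages.

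A reader might also take a doubling of the related-TEAE rate as the expected effect. That needs a flat hazard to Day 39. About 0.8% of LOXO-292 remains at Day 30, and omeprazole ends on Day 29. Protocol Appendix 1 also requires a time course compatible with causation before an event is called related. The true excess may be close to nothing.

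There is a reason to credit late events to the combination. Omeprazole is a study drug in Period 3 (Protocol 5.1, Table 3), and Protocol 3.2 notes that its effect on acid secretion may be prolonged. A related event after Day 29 can fairly be linked to the last treatment given.

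All AEs are listed, so aligned counts could be rebuilt by hand. The table shells are a separate document and may already footnote this. Equal windows would also leave treatment confounded with period and, in Period 3, with the meal.

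These arguments limit the consequence and I accept them. They do not remove the mismatch in the stated counting rule. The day-of-onset summary covers only the multiple-dosing period and does not realign the treatment columns.

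**Conclusion.** The mismatch is real. For completers, two LOXO-292 windows run 7 days and the third runs 12 to 16, with the last 5 to 9 days limited to related events and SAEs. Only that column mixes two collection rules, and its related-TEAE frequency can be raised by window length alone.

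The size is uncertain. From an assumed 10% risk over 7 days it ranges from about 10.1% to 21.4%. The constant-hazard figures are an upper bound, provided the hazard does not rise after dosing ends.

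It would go too far to say that the columns cannot be compared at all, or that the table is known to disfavour the omeprazole combination. Days 23 to 30 already match the other windows, and the rest depends on whether related events occur after EOT. Minor severity.

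**What to change.** In SAP 10.4.1, for the by-treatment TEAE tables, count LOXO-292 + omeprazole events from Day 23 dosing to Day 30/EOT. Show onsets from EOT to Follow-up in a separate column labelled as follow-up after LOXO-292 + omeprazole, and keep them in the overall total and the listings. The three LOXO-292 columns then each cover 7 days under one collection rule, and the link to the last treatment stays visible.

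The cost is a change to one SAP sentence and one extra table column. Data collection does not change. The downside is that a late related event appears outside the main treatment column, which the label is meant to offset.

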10.4.2 Concomitant medication

Concomitant medication will be coded using the World Health Organization drug dictionary (WHODrug Global B3, 01 March 2019). Concomitant medication will be listed.

10.4.3 Clinical Laboratory Parameters

Clinical chemistry, hematology and coagulation data will be summarized by parameter and treatment, together with changes from baseline. In addition, all clinical chemistry, hematology, coagulation and urinalysis data outside the clinical reference ranges will be listed by parameter and treatment.

Values for any clinical chemistry, hematology, coagulation and urinalysis values outside the clinical reference ranges will be flagged on the individual subject data listings.

10.4.4 Vital Signs

The vital signs data will be summarized by treatment, together with changes from baseline. Vital signs values outside the clinical reference ranges will be flagged on the individual subject data listings.

10.4.5 Electrocardiogram

The ECG data will be obtained directly from the 12-lead ECG tracings. These data include the QT interval calculated using the Fridericia correction (QTcF), the PR, RR and QT intervals, the QRS duration, and heart rate.

Changes from baseline will be calculated. Values for ECG parameters outside the clinical reference ranges will be flagged, including $QTcF > 450$ msec and change from baseline > 30 msec, on the individual subject data listings.

The ECG data will be summarized and listed by treatment, together with changes from baseline.

10.4.6 Other Assessments

All other safety assessments not detailed in this section will be listed but not summarized or statistically analyzed.

10.4.7 Safety and Tolerability Statistical Methodology

No inferential statistical analyses are planned

11 INTERIM ANALYSES

No interim statistical analyses are planned.

12 CHANGES FROM THE PROTOCOL SPECIFIED STATISTICAL ANALYSES

There were no changes from the protocol-specified statistical analyses.

13 DATA PRESENTATION

13.1 Insufficient Data for Presentation

Some of the TFLs may not have sufficient numbers of subjects or data for presentation. If this occurs, the blank TFL shell will be presented with a message printed in the center of the table, such as, "No serious adverse events occurred for this study."

